Based on prior studies, we do not anticipate clinically significant adverse effects associated with the administration of H₂-enriched water. Several published studies have administered H₂-enriched drinking water or IV saline to human subjects without observing any serious treatment-associated adverse events. Nakao and colleagues administered 1.5 – 2 L of H₂-enriched water daily for a total of 8 weeks to 20 subjects with potential metabolic syndrome. They observed a small decrease in high density lipoprotein, but no abnormalities in weight, blood pressure, hematological parameters or routine clinical chemistry values²⁶. No serious adverse events were noted. Four subjects exhibited mild AEs (1 headache, 1 heartburn, 3 loose stools), but no definitive relationship to treatment could be established. Ishibashi and colleagues administered H₂-enriched IV saline (500 mL qday x 5 days, approximately 1.6 ppm H₂) to 20 normal volunteers to assess safety; researchers reported lack of clinical AEs, and lack of abnormalities detected on routine hematology and blood chemistry²⁷.

The proposed administration of 250 mL BID of PO water to subjects with Parkinson's disease should not pose significant risk. This volume is less than needed to keep a patient hydrated. Any subject whose attending physician is concerned about study medication-associated fluid overload would be excluded from the study, as per the exclusion criteria.

The risks associated with the blood draw included in this study include temporary pain and bruising where the needle enters the skin, possible fainting, and small chance of infection.

We will ask subjects on parkinsonian medication to refrain from taking their parkinsonian medication for 12 hours prior to the baseline and 56-week visits. This is not expected to contribute any significant risk, as hundreds of studies have been conducted using this procedure. Subjects will sign on the consent form that they understand this procedure and are comfortable with it.

G 2. Adequacy of Protection against Risks

Although the risks of the H₂ therapy proposed here are more than minimal, they should not pose significant risk. The PI and Data Safety Monitor will monitor safety and risks throughout the study (see section G 1).

Signed informed consent will be obtained from each subject. A copy of the consent form countersigned by study staff will be provided to the subject.

The PI and all key personnel involved in the study will have completed the Collaborative IRB training initiative and HIPAA training. The PI will be responsible for reporting adverse events experienced by study subjects to the IRB according to IRB guidelines.

Confidentiality will be maintained. All subject research data will be coded with subject ID number. Paper files will be kept in a secure, locked area. The electronic database used during the study will be secured with a password and saved on a secured shared drive only accessible to key

personnel. Subject results will never be discussed in any form in the presence of other subjects in the study, or with non-laboratory personnel. Subjects' names will not be used in manuscripts or presentations about this research.

G3. Potential Benefits of Proposed Research to the Subject and Others

The proposed therapy may slow the progression of Parkinson's disease, a common neurodegenerative disorder for which disease-modifying treatment is not currently available. Even if the study is negative, observations made during the study may aid the development of future neuroprotective trials.

H. DATA SAFETY MONITORING PLAN

H 1. Adverse events monitoring

[name], who is unaffiliated with the current study, has volunteered to serve as our data safety monitor (DSM). [name] is Professor and Vice Chair (Clinical Affairs) in the Department of Neurology here at Stony Brook. [name] will be unblinded to treatment. Assisted by study staff, she will periodically review the protocol documentation and safety data. The first review will occur after the first 5 subjects have been enrolled and on study drug for >6 weeks. Additional reviews will then take place quarterly. Among the important goals of the reviews will be to ensure that adverse events are reported, protocol amendments are filed with the IRB, inclusion/exclusion criteria are followed. If in the DSM's judgement a pattern of unexpected and clinically serious adverse events emerges, or if protocol compliance is inadequate, the study will be terminated.

Any unfavorable and unintended symptom, sign (including a clinically significant abnormal laboratory finding) or disease that is temporally associated with a study will be considered a study AE. The study staff will carefully monitor each subject throughout the study for possible AEs, and document such in an AE log. Minimum information recorded for each AE includes type of event, duration (start and end dates), severity, seriousness, causality to study drug, action taken, and outcome. The PI or one of the Co-Is will grade the severity of AEs based on the DHHS/NIH Common Terminology Criteria for Adverse Events (CTCAE) v4.0. Baseline parkinsonian symptoms and signs documented prior to initiation of study medication will not be considered AEs. The PI will proactively bring to DSM attention any serious AEs judged possibly associated with study medication. Any unexpected fatal or life-threatening suspected adverse reactions will be reported to the FDA within 7 calendar days.

Table 6: Schedule for safety monitoring and assessments

	Assessments	Frequency
--	--------------------	------------------

H ₂ tablet and placebo	Stony Brook pharmacy will bottle tablets following USP 797 guidelines	At each preparation
Study safety	The Data Safety Monitor will review adverse events and protocol compliance	At the first 5 patients enrolled and on study drug > 6 weeks; proactive reviews will then take place quarterly

H 2. Data safety

All paper study data will be kept in secure, locked cabinets. All identifiable electronic study data will be password-protected and saved in Redcap and/or in a secure shared drive on the Stony Brook server only accessible by study staff. The study coordinator will check the data for accuracy. Missing data will be identified and obtained (if possible) in a timely fashion. Study staff will take steps to ensure that all information obtained is kept private. The subjects' names will not be used whenever possible. Study staff will instead use study codes lacking PHI. The electronic data will be banked on the same secure server after the study ends. The study staff may submit a new proposal to obtain approval from the IRB to use this data.

REFERENCES

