A recent small pilot randomized double-blind placebo-controlled trial involving a total of 17 patients with idiopathic PD treated with levodopa (Hoehn & Yahr stages I – IV; average disease duration of 6.5 and 7.2 years for active treatment and placebo arms, respectively) demonstrated that drinking 1000 mL/day of H₂-enriched water for a total of 48 weeks was safe and well-tolerated in this patient cohort, with no adverse events reported. Notably, patients in the active treatment arm demonstrated significant improvement in total scores on the Unified Parkinson's Disease Rating Scale (UPDRS) when compared to placebo (-5.7 ± 8.4 vs. 4.1 ± 9.2 for active treatment vs. placebo, respectively). Changes in the motor subscale of the UPDRS (UPDRS-III), a secondary outcome measure, trended towards significance (-5.8 ± 7.2 vs. 2.3 ± 8.5 for active treatment vs. placebo, respectively; p = 0.074)¹³. Despite the promising results from this small pilot study, its design is inherently unable to differentiate between disease-modifying and symptomatic effect. Additionally, the recruited patients were relatively advanced in the course of their disease, when the pool of existing dopaminergic neurons was likely quite low, and the disease-modifying potential for the treatment therefore diminished.

A follow-up randomized double-blind placebo-controlled multi-center trial to assess the efficacy of H₂ in a larger sample of PD patients, including those not on levodopa, is currently underway.¹⁴ Several aspects of the design of this ongoing study are concerning, however. Enrolled patients had an average disease duration of 6.8 ± 4.5 years at time of study onset, indicating that many of the study participants have a small pool of salvageable dopaminergic neurons. In addition, the H₂-enriched water provided to patients in this study is distributed weekly in plastic bottles, through which H₂ is able to rapidly diffuse over a period of minutes to hours. The H₂ concentration at the time of consumption is thus unclear.

Here, we propose a double-blind placebo-controlled study to investigate the safety and tolerability, and to explore the efficacy, of H₂-enriched water in a population of early-stage PD

patients. We seek to enroll a total of 70 patients with early-stage PD, and will make use of a practical method our department has considerable experience with in order to generate H₂-enriched water.

D. RESEARCH DESIGN AND METHODS

D1. Rationale/Overview

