The baseline visit will occur no more than 4 weeks after the screening visit, and may occur on the same day as the screening visit if the patient is not taking dopaminergic medication.

The following data will be collected at the baseline visit.

Table 2. Baseline data

Data	Detail
General health status	Physical examination findings Neurological examination findings Concomitant medications (including review of use of over the counter and prescription medications containing magnesium) Height, weight, orthostatic vital signs*
PD symptom burden	Total Unified Parkinson's Disease Rating Scale (MDS-UPDRS) score (parts I – IV)
Health-related quality of life	Parkinson's Disease Questionnaire-39 (PDQ-39)
PD stage	Modified Hoehn & Yahr staging
Cognitive status	Montreal Cognitive Assessment (MoCA)
Emotional status	Geriatric Depression Scale – short form (GDS-15)
Uric acid	Blood draw

If subjects are taking parkinsonian medication, we will ask them to be off this medication for at least 12 hours prior to their baseline visit in order to perform assessment of their motor symptoms (MDS-UPDRS part III) and PD stage (Modified Hoehn & Yahr) in the practically defined “off” medication state. This is a standard procedure for this type of study²³. Subjects must be willing to undergo this washout procedure to participate in the study. Assessment of cognitive status will also be performed in the practically defined “off” medication state. After motor assessment and PD staging is performed in the “off” state, patient will be instructed to take his/her parkinsonian medication in the office. The motor subscale (MDS-UPDRS part III) will then be performed, and PD stage (Modified Hoehn & Yahr) will be assessed, in the best

“on” state (best response to morning dose of antiparkinsonian drug) 30-60 minutes after medication has been taken.

* Orthostatic vital signs will be obtained by measuring vital signs after 5 minutes supine and after 2 minutes standing. We will obtain 3 sets of orthostatic vital signs at least 15-20 minutes apart. The average of the 3 orthostatic vital signs measurements will be used for comparison to all post-treatment measurements.

Subjects will be instructed to avoid the regular use of over the counter antacids, laxatives, and cathartics that contain magnesium while taking study medication.

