Serum uric acid level will be drawn at the baseline visit given evidence suggesting that there may be an inverse relationship between levels of uric acid and rate of PD progression^{7,8}. Uric acid level is for research purposes only.

The PI or co-investigator will once again review the inclusion/exclusion checklist at the time of the baseline visit.

D5. d. Treatment assignment & administration

For subjects meeting enrollment criteria and providing consent, treatment with H₂-enriched water or placebo will begin after the baseline visit. The subject will be randomly assigned to either the active treatment or the placebo group. A blocked randomization list will be generated using the following website: <https://www.sealedenvelope.com/simple-randomiser/v1/lists>. The research pharmacist will be responsible for using the generated list to assign treatment to subjects as they are enrolled. The study staff assessing study outcomes will remain blinded to treatment assignment. The study doctor will dispense study drug to the subject. Masking of active and placebo treatment will be maintained by bottling tablets in containers that appear identical.

The medication will be administered orally as 250 mL BID of H₂-enriched or placebo drinking water. Subjects will be instructed to adhere to a q6h – q10h schedule, but for convenience a dose may be taken a few hours earlier or later, as there is no expected mechanism of action indicating that dose timing would be critical for efficacy.

D5. e. Follow-up visits

Follow-up visits will be scheduled to occur at weeks 8, 24, 40, 52, and 56 (\pm 4 weeks). Adverse effects will be monitored to assess safety and tolerability in this patient population. The study doctor will dispense study drug to patient at weeks 8, 24, and 40. The subject will be counseled to call the investigator immediately to report the occurrence of any adverse events. Subjects will be instructed to return bottles with unused tablets at each follow-up visit. Tablet counts will be performed by the research pharmacist to monitor patient compliance.

As a temporary measure to allow for continuity of this study during the COVID-19 pandemic, follow-up visits will be conducted remotely via telephone and/or secure videoconferencing using

the Microsoft Teams application. The following modifications will be made to follow-up visits during this time period:

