1. The study medication will be mailed to the subject instead of given to them in person. The study coordinator will pick up the medication from the research pharmacy at least 4 days prior to the follow-up visit and bring it to the Stony Brook Post Office and have it shipped via Priority Mail. The study coordinator will email the subject the day that the medication goes out by mail to let them know to look for it and will request that the subject email or call to confirm once they have received it. The study coordinator will call two days after the medication has been shipped to confirm it was received if the subject has not called by then.
2. Instead of bringing the old container of study medication to the follow-up visit, subjects will be instructed to count the number of tablets in the container the morning of their follow-up visit (after taking the morning dose for that day) and reporting that number to the researcher during their follow-up visit. They will also be instructed to bring the container to their next in-person visit.
3. Patients will not receive a physical examination or neurological examination. While these examinations do provide some meaningful information, they are not necessary for the primary and secondary outcomes of the study.
4. A modified version of the motor portion of the Unified Parkinson's Disease Rating Scale (MDS-UPDRS III) will be performed remotely with the exception of rigidity testing and postural instability testing which both require hands-on assessment by the rater. The modified UPDRS (mUPDRS) has demonstrated evidence of validity and reliability.²⁴
5. A modified version of the Montreal Cognitive Assessment (MoCA) will be administered. Performing the MoCA remotely via telemedicine has been shown to be feasible in movement disorders populations.²⁵
6. Survey based assessments (MDS-UPDRS I, II, IV, GDS-15, and PDQ-39) will be administered online via RedCap.
7. Height and weight will be measured by the subject, if they have the ability to do so, and reported during their visit. A notation will be added to the dataset indicating that these were measured by the subject since these measures may not be consistent with those that would have been obtained at the clinical research center.

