8. Instructions for measuring orthostatic vital signs will be provided to subjects prior to the follow-up visit. If they have a means for measuring blood pressure they will take these measurements and report them at their visit. A notation will be added to the dataset indicating that these were measured by the subject since these measures may not be consistent with those that would have been obtained at the clinical research center.
9. The research coordinator will call subjects weekly to inquire about adverse events beginning the week after the remote visit has taken place as a safeguard given the inability to conduct a physical and neurological exam and to have the research nurse measure orthostatic vital signs. Weekly calls will continue until the next in-person visit has taken place.
10. If restrictions due to COVID-19 are lifted within 4 weeks of the remote visit, an in-person visit will be scheduled and the physical examination, neurological examination, MDS-UPDRS III, Hoehn and Yahr Staging, and orthostatic vital signs will be taken during this visit.

11. Subjects will be sent a new consent form and have the changes reviewed by phone. They will be asked to sign the consent form and return via email or paper mail. Once received, the form will be signed by the study team member obtaining consent and sent back to the subject.

The following data will be collected at follow-up visits at weeks 8, 24, 40 and 52.

Table 3. Follow-up data at weeks 8, 24, 40 and 52

Data	Detail
General health status	Physical examination findings ^a Neurological examination findings ^a Concomitant medications Height, weight, orthostatic vital signs ^b
PD motor symptoms	MDS-UPDRS part III ^c

The following modifications will be made for visits taking place remotely, as will be required during the COVID-19 pandemic:

^aThese measurements will not take place for visits taking place remotely

^bThese measures will be taken by the subject, if they have the capacity to do so, for visits taking place remotely

^cA modified version of this measure will be administered for visits taking place remotely

Orthostatic vital signs will be obtained by measuring vital signs after 5 minutes supine and after 2 minutes standing.

The following data will be collected at the follow-up visit at week 56.

Table 4. Follow-up data at week 56

Data	Detail

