1. **Motor Symptoms:** To investigate the effect of H₂-enriched water on the progression of motor symptoms in PD patients. Progression of motor symptoms will be assessed by change in the motor subscale of the MDS-Unified Parkinson's Disease Rating Scale (MDS-UPDRS-III) from baseline to week 56. This will be assessed in the “off” state.
2. **Quality of life:** To investigate the effect of H₂-enriched water on health-related quality of life in PD patients. Health-related quality of life will be assessed by change in the PDQ-39 from baseline to week 56.
3. **Cognitive Function:** To investigate the effect of H₂-enriched water on the progression of cognitive decline in PD patients. Cognitive function will be assessed using the Montreal Cognitive Assessment (MoCA) scale at baseline and week 56. This will be assessed in the “off” state.
4. **PD Symptom Burden:** To investigate the effect of H₂-enriched water on the progression of symptom burden in PD patients. Progression of symptom burden will be assessed by change in the Total MDS-UPDRS from baseline to week 56.

D8. Enrollment Failure

Subject enrollment will be examined continuously. Our goal is to enroll the targeted 70 subjects within 3 years of enrolling the first subject. If enrollment rate by the end of 18 months is not on

track towards approaching this goal, and no prospects for enhancing enrollment are on the horizon (for example, through partnership with another medical center or network), we will terminate the study and analyze outcomes based upon subjects enrolled at that point. If enrollment is proceeding well, but a reasonable extension of time is needed to complete enrollment of the targeted 70 subjects, we will submit an appropriate amendment request to the IRB prior to the end of the 3 year time frame.

E. STATISTICS

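### Remote week-56 Part III scores omit items that the baseline includes, and D7b does not say how change is then computed

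*Combined protocol and SAP*

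**What the plan says.** Table 2 (D5.c, Baseline visit) lists the "Total Unified Parkinson's Disease Rating Scale (MDS-UPDRS) score", parts I to IV, with no remote variant. The COVID-19 modifications in D5.e apply to follow-up visits only. Modification 4 has Part III performed remotely "with the exception of rigidity testing and postural instability testing which both require hands-on assessment by the rater". Table 4 footnote c and Table 5 footnote d apply the modified version to week 56, the endpoint visit.

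D7b, outcome 1: "Progression of motor symptoms will be assessed by change in the motor subscale" of the MDS-UPDRS, baseline to week 56, off medication. D7b, outcome 4: "Progression of symptom burden will be assessed by change in the Total MDS-UPDRS from baseline to week 56". Neither mentions the modified version. Section E gives no rule for it: no common-item score, prorating, imputation, sensitivity analysis or adjustment for visit mode.

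Two passages come close. Modification 4 states that the modified scale has evidence of validity and reliability. Modification 10 says: "If restrictions due to COVID-19 are lifted within 4 weeks of the remote visit, an in-person visit will be scheduled", and that visit includes a full Part III. It does not say which of the two scores is analysed.

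**The concern.** A change score needs the same items at both ends. Here the baseline holds rigidity and postural points that a remote week-56 score cannot hold. Two secondary outcomes would then mix subjects measured on one item set with subjects measured on two.

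The protocol considers this kind of loss elsewhere. Modification 3 drops the physical and neurological examinations because "they are not necessary for the primary and secondary outcomes of the study", and self-measured height, weight and vital signs are to be flagged in the dataset. The omitted Part III items do belong to two secondary outcomes, yet they get neither a flag nor a scoring rule.

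At stake are the reading of progression within each arm and the precision of the motor comparison, on which Section E bases the sample size. Without a rule, the choice among literal, matched, prorated or in-person-only scores could be made after the data are seen.

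**Working it through.** **Identity.** Let C be the common items and O the omitted items (rigidity, postural stability), at week 0 and week 56.

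- Full change = (C56 + O56) − (C0 + O0).
- Remote change, if D7b is applied to the scores collected = C56 − (C0 + O0) = common-item change − O0 = full change − O56.

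O cannot be negative, so the shift is always towards apparent improvement. With remote share f and mean omitted points R, the within-arm mean shifts by −f × R.

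**Plan's own figure.** Section E states 60 subjects for 90% power at two-sided alpha 0.01. Section C gives the pilot's UPDRS-III changes as minus "5.8 ± 7.2 vs. 2.3 ± 8.5 for active treatment vs. placebo, respectively". Difference = 2.3 + 5.8 = 8.1; SD = √((7.2² + 8.5²)/2) = √62.045 = 7.88. A two-sample t-test then needs N = 60, with power 90.2% at 30 per arm, so the stated 60 is reproduced. The figures printed in Section E (−5.7 ± 8.4 vs. 4.1 ± 9.2) are those Section C gives for total UPDRS, and they lead to N = 52. I therefore use 8.1 and 7.88.

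**Assumptions, none from the documents.** R = 2 to 8 points; f = 10%, 25%, 50% or 75%; SD of omitted points kR with k = 0, 0.5 or 0.75; correlation ρ between omitted points and true change of 0 or, where k > 0, 0.3; no drug effect on the omitted items.

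**Within-arm shift.** At f = 10%: −0.2 to −0.8 points. At f = 25-75%: −0.5 (0.25 × 2) to −6 (0.75 × 8). For scale, the pilot's placebo UPDRS-III change was +2.3 (older scale, more advanced patients). The shift cancels a change of that size when R = 2.3/f, which is 9.2, 4.6 or 3.1 at 25%, 50% or 75% remote.

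**Variance and power.** Var = 62.045 + f(1−f)R² + f(kR)² − 2fρ(7.88)kR; noncentral t, 30 per arm, alpha 0.01.

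- Middle case, f = 0.5, R = 4, k = 0.5, ρ = 0: 62.045 + 4 + 2 = 68.045, SD 8.25, power 86.8%.
- Worst case, f = 0.75, R = 8, k = 0.75, ρ = 0: 62.045 + 12 + 27 = 101.045, SD 10.05, power 67.6%.
- Best case, f = 0.75, R = 2, k = 0.75, ρ = 0.3: 62.045 + 0.75 + 1.69 − 5.32 = 59.17, SD 7.69, power 91.7%.

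| R | Power, 10% remote | Power, 25-75% remote |
|---|---|---|
| 2 | 89.9-90.2% | 88.8-91.7% |
| 4 | 88.9-89.7% | 84.6-90.8% |
| 6 | 87.2-88.7% | 77.3-88.6% |
| 8 | 84.8-87.1% | 67.6-84.6% |

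**Between arms.** With equal f and no drug effect on the omitted items, the shift cancels (simulated null rejection 1.00-1.03% at nominal 1%). If remote shares differ, bias = R × gap: 0.2-0.8 points for a 10-point gap and 0.4-1.6 for a 20-point gap. Null rejection is then 1.03-1.46% and 1.14-3.03% (k = 0.5, ρ = 0.3, average f = 0.5). If instead the omitted items carry 10-20% of the 8.1 difference, half remote removes 0.5 × 0.10 × 8.1 = 0.41 to 0.5 × 0.20 × 8.1 = 0.81 points.

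**The case against.** **D7b does not order this subtraction.** This stands. D7b names the MDS-UPDRS-III, and the remote version has its own name (mUPDRS). One could read a remote visit as giving no MDS-UPDRS-III total, or assume that an analyst would match items. A reader might infer that the plan instructs a wrong calculation, but the text is only silent. The artefact follows if the stated change score is applied to the scores collected.

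**Randomisation protects the comparison.** Largely true. D5.d says "A blocked randomization list will be generated using the following website", allocation is 1:1, and similar remote shares are likely, though unequal drop-out could disturb them. A reader might infer a biased treatment effect, but the documents give no reason to expect unequal shares or a drug effect confined to these items.

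**The large power losses are assumed.** True. The 67.6% figure needs R = 8, 75% remote, SD 0.75R and zero correlation together, in patients within 3 years of diagnosis and below Hoehn & Yahr stage III. Remote visits are described as temporary, and recruitment is projected over 3 years, so low remote shares are plausible. The documents do not support a claim that the trial is underpowered for this reason.

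**The protocol already deals with it.** Only in part. Validity of a short scale does not make it subtractable from a full-scale baseline. Modification 10 helps only if restrictions lift within 4 weeks and only if the repeat score is the one analysed.

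**Conclusion.** The concern holds as an unresolved mismatch of item sets in two secondary outcomes. Its direction is certain if the plain change score is used: remote subjects appear to progress less than they did, by their omitted points. Its size is not known, since neither the omitted points nor the remote share is in the documents. Under the stated assumptions the effect on power runs from none (or a slight gain, when omitted points correlate positively with true change) to material, and at 10% remote it is at most 5.4 percentage points (90.2 − 84.8). Bias between arms is nil with equal remote shares and no drug effect on the omitted items.

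The safety and tolerability outcomes are untouched, and the efficacy analyses are exploratory. It should still be fixed: the motor score drives the sample size, the results are meant to inform a phase 3 decision, and the repair is cheap.

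**What to change.** Amend D7b and Section E before unblinding:

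1. When the week-56 Part III is the remote version, compute change in Part III, and in the Part III component of Total MDS-UPDRS, only on items rated at both visits. A modified score is then never subtracted from a full-scale baseline.
2. State that an in-person repeat under modification 10, where done, supplies the full-scale score.
3. Tabulate the remote share by arm. Pooled remote share and baseline omitted points can be tabulated from blinded data, although baseline points only approximate those at week 56.
4. Report as sensitivity analyses (a) the common-item score for all subjects and (b) full Part III change in subjects with an in-person final assessment.
5. Fix in advance whether the main comparison uses the common-item score for everyone or matched scores with adjustment for visit mode. That choice is the sponsor's.

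**Cost.** Wording and one derived variable, provided item-level baseline scores are available. Matching removes the level of the omitted items but not their change (O56 − O0), so remote subjects still contribute nothing on rigidity or postural stability. Using the common-item score for everyone removes that inconsistency too, but drops rigidity, a cardinal sign in the inclusion criteria, from the main comparison. If the omitted items carried 10% or 20% of the 8.1 difference (assumed), power would lie between 81.7% or 69.8% (SD unchanged) and 90.2% (SD shrinking in proportion). These figures are not like for like with the power table, which assumes no drug effect on those items, so they do not rank the options.
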